7.1.3. COVID-19

If a participant has COVID-19 during the study, this should be reported as an AE or SAE (as appropriate) and appropriate medical intervention provided. Temporary discontinuation of the study intervention may be medically appropriate until the participant has recovered from COVID-19.

It is recommended that the investigator discuss temporary or permanent discontinuation of study intervention with the study medical monitor.

7.2. Participant Discontinuation/Withdrawal From the Study

A participant may withdraw from the study at any time at their own request. Reasons for discontinuation from the study include the following:

- Refused further study procedures;
- Lost to follow-up;
- Death;
- Study terminated by sponsor;
- Pregnancy;
- Behavioral, compliance, or administrative reasons.

At the time of discontinuing from the study, if possible, an early discontinuation visit should be conducted. See the [SoA](#) for assessments to be collected at the time of study discontinuation and follow-up and for any further evaluations that need to be completed.

The early discontinuation visit applies only to participants who are enrolled/randomized and then are prematurely withdrawn from the study. Participants should be questioned regarding their reason for withdrawal.

The participant will be permanently discontinued from the study intervention and the study at that time.

If a participant withdraws from the study, they may request destruction of any remaining samples taken and not tested, and the investigator must document any such requests in the site study records and notify the sponsor accordingly.

If the participant withdraws from the study and also withdraws consent (see Section 7.2.1) for disclosure of future information, no further evaluations will be performed and no additional data will be collected. The sponsor may retain and continue to use any data collected before such withdrawal of consent.

7.2.1. Withdrawal of Consent

Participants who request to discontinue receipt of study intervention will remain in the study and must continue to be followed for protocol-specified follow-up procedures. The only exception to this is when a participant specifically withdraws consent for any further contact with them or persons previously authorized by the participant to provide this information. Participants should notify the investigator in writing of the decision to withdraw consent from future follow-up, whenever possible. The withdrawal of consent should be explained in detail in the medical records by the investigator, as to whether the withdrawal is only from further receipt of study intervention or also from study procedures and/or posttreatment study

follow-up, and entered on the appropriate CRF page. In the event that vital status (whether the participant is alive or dead) is being measured, publicly available information should be used to determine vital status only as appropriately directed in accordance with local law.

7.3. Lost to Follow-up

A participant will be considered lost to follow-up if the participant repeatedly fails to return for scheduled visits and is unable to be contacted by the study site.

The following actions must be taken if a participant fails to return to the clinic for a required study visit:

- The site must attempt to contact the participant and reschedule the missed visit as soon as possible. Counsel the participant on the importance of maintaining the assigned visit schedule and ascertain whether the participant wishes to and/or should continue in the study;
- Before a participant is deemed lost to follow-up, the investigator or designee must make every effort to regain contact with the participant (where possible, 3 telephone calls and, if necessary, a certified letter to the participant's last known mailing address or local equivalent methods). These contact attempts should be documented in the participant's medical record;
- Should the participant continue to be unreachable, the participant will be considered to have withdrawn from the study.

8. STUDY ASSESSMENTS AND PROCEDURES

8.1. Administrative and Baseline Procedures

The investigator (or an appropriate delegate at the investigator site) must obtain a signed and dated ICD before performing any study-specific procedures.

Study procedures and their timing are summarized in the [SoA](#). Protocol waivers or exemptions are not allowed.

Adherence to the study design requirements, including those specified in the [SoA](#), is essential and required for study conduct.

All screening evaluations must be completed and reviewed to confirm that potential participants meet all eligibility criteria. The investigator will maintain a screening log to record details of all participants screened and to confirm eligibility or record reasons for screening failure, as applicable.

Participants will be screened within 28 days prior to administration of the study intervention to confirm that they meet the study population criteria for the study. If the time between screening and dosing exceeds 28 days as a result of unexpected delays (eg, delayed drug

shipment), then participants do not require rescreening if the laboratory results obtained prior to first dose administration meet eligibility criteria.

A participant who qualified for this protocol but did not enroll from an earlier cohort/group may be used in a subsequent cohort/group without rescreening, provided laboratory results obtained prior to the first dose administration meet eligibility criteria for this study. In addition, other clinical assessments or specimen collections, eg, retained research samples, may be used without repeat collection, as appropriate.

Every effort should be made to ensure that protocol-required tests and procedures are completed as described. However, it is anticipated that from time to time there may be circumstances outside the control of the investigator that make it unfeasible to perform the test. In these cases, the investigator must take all steps necessary to ensure the safety and well-being of the participant. When a protocol-required test cannot be performed, the investigator will document the reason for the missed test and any corrective and preventive actions that they have taken to ensure that required processes are adhered to as soon as possible. The study team must be informed of these incidents in a timely manner.

Safety/laboratory/analyte results that have been collected for the purposes of this study and could unblind the study will not be reported to investigative sites or other blinded personnel until the study has been unblinded.

If an IV catheter is utilized for blood sample collections, ECGs and vital sign assessments (pulse rate and BP) should be collected prior to the insertion of the catheter.

For samples being collected and shipped, detailed collection, processing, storage, and shipment instructions and contact information will be provided to the investigator site prior to initiation of the study.

The total blood sampling volume for individual participants in this study is approximately 340 mL. The actual collection times of blood sampling may change. Additional blood samples may be taken for safety assessments at times specified by Pfizer, provided the total volume taken during the study does not exceed 550 mL during any period of 56 consecutive days.

To prepare for study participation, participants will be instructed on the information in the Lifestyle Considerations and Concomitant Therapy sections of the protocol.

8.1.1. Baseline Procedures

Planned timepoints for medical history and demography are provided in the [SoA](#).

8.2. Efficacy Assessments

Not Applicable.

8.3. Safety Assessments

Planned time points for all safety assessments are provided in the [SoA](#). Unscheduled safety measurements may be obtained at any time during the study to assess any perceived safety issues.

8.3.1. Physical Examinations

A complete physical examination will include, at a minimum, head, ears, eyes, nose, mouth, skin, heart and lung examinations, lymph nodes, and gastrointestinal, musculoskeletal, and neurological systems.

A brief physical examination will include, at a minimum, assessments of general appearance, the respiratory and cardiovascular systems, and participant-reported symptoms.

Physical examinations may be conducted by a physician, trained physician's assistant, or nurse practitioner as acceptable according to local regulation.

Height and weight will also be measured and recorded as per the [SoA](#). For measuring weight, a scale with appropriate range and resolution is used and must be placed on a stable, flat surface. Participants must remove shoes, bulky layers of clothing, and jackets so that only light clothing remains. They must also remove the contents of their pockets and remain still during measurement of weight.

Physical examination findings collected during the study will be considered source data and will not be required to be reported, unless otherwise noted. Any untoward physical examination findings that are identified during the active collection period and meet the definition of an AE or SAE ([Appendix 3](#)) must be reported according to the processes in [Sections 8.4.1 to 8.4.3](#).

8.3.2. Vital Signs

8.3.2.1. Blood Pressure and Pulse Rate

Supine BP will be measured with the participant's arm supported at the level of the heart and recorded to the nearest mm Hg after approximately 5 minutes of rest. The same arm (preferably the dominant arm) will be used throughout the study. Participants should be instructed not to speak during measurements.

The same properly sized and calibrated BP cuff will be used to measure BP each time. The use of an automated device for measuring BP and pulse rate is acceptable; however, when done manually, pulse rate will be measured in the brachial/radial artery for at least 30 seconds. When the timing of these measurements coincides with a blood collection, BP and pulse rate should be obtained prior to the nominal time of the blood collection.

Additional collection times, or changes to collection times, of BP and pulse rate will be permitted, as necessary, to ensure appropriate collection of safety data.

Any untoward vital sign findings that are identified during the active collection period and meet the definition of an AE or SAE ([Appendix 3](#)) must be reported according to the processes in [Sections 8.4.1 to 8.4.3](#).

8.3.3. Electrocardiograms

Standard 12-lead ECGs utilizing limb leads (with a 10-second rhythm strip) should be collected at times specified in the [SoA](#) section of this protocol using an ECG machine that automatically calculates the HR and measures PR interval, QT interval, QTcF, and QRS complex. Alternative lead placement methodology using torso leads (eg, Mason-Likar) should not be used given the potential risk of discrepancies with ECGs acquired using standard limb lead placement. All scheduled ECGs should be performed after the participant has rested quietly for at least 5 minutes in a supine position.

3 baseline pre-dose measurements are needed for CQT analysis, these ECGs will be done approximately 30 min, 20 min, and 10 min before the pre-dose meal in Periods 1 and 2, and approximately 30 min, 20 min, and 10 min pre-dose in Period 3. The average of the triplicate ECGs over the 3 pre-dose measurements (total of 9 ECGs) will serve as each participant's baseline QTc value. Triplicate 12-lead ECGs will be obtained approximately 2 to 4 minutes apart.

To ensure safety of the participants, a qualified individual at the investigator site will make comparisons to baseline measurements. Additional ECG monitoring will occur if a) a postdose QTcF interval is increased by ≥ 60 ms from the baseline **and** is > 450 ms; or b) an absolute QT value is ≥ 500 ms for any scheduled ECG. If either of these conditions occurs, then 2 additional ECGs will be collected approximately 2 to 4 minutes apart to confirm the original measurement. If the QTcF values from these repeated ECGs remain above the threshold value, then a single ECG must be repeated at least hourly until QTc values from 2 successive ECGs fall below the threshold value that triggered the repeat measurement.

To ensure safety of the participants, a qualified individual at the investigator site will make comparisons to baseline measurements. Additional ECG monitoring will occur if a) the mean value from the triplicate measurements for any postdose QTcF interval is increased by ≥ 60 ms from the baseline **and** is > 450 ms; or b) an absolute QT value is ≥ 500 ms for any scheduled ECG. If either of these conditions occurs, then a single ECG measurement must be repeated at least hourly until QTcF values from 2 successive ECGs fall below the threshold value that triggered the repeat measurement.

If a) a postdose QTcF interval remains ≥ 60 ms from the baseline **and** is > 450 ms; or b) an absolute QT value is ≥ 500 ms for any scheduled ECG for greater than 4 hours (or sooner, at the discretion of the investigator); or c) QTcF value get progressively longer, the participant should undergo continuous ECG monitoring. A cardiologist should be consulted if QTcF values do not return to less than the criteria listed above after 8 hours of monitoring (or sooner, at the discretion of the investigator).

In some cases, it may be appropriate to repeat abnormal ECGs to rule out improper lead placement as contributing to the ECG abnormality. It is important that leads be placed in the same positions each time in order to achieve precise ECG recordings. If a machine-read QTc value is prolonged, as defined above, repeat measurements may not be necessary if a qualified medical provider's interpretation determines that the QTcF values are in the acceptable range.

ECG values of potential clinical concern are listed in [Appendix 8](#).

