Contraception check	X	X						X		X	X	Contraception check will occur with discharge activities at the end of Period 7.
FSH (post-menopausal women only)	X											
Urine drug testing	X	X										
12-Lead ECG (triplicate)	X		X				X	X	X		X	
 Single ECG for Screening. Pre-dose ECGs are triplicate of triplicates at 30 min, 20 min, and 10 min before the pre-dose meal in Periods I and 2, and 30 min, 20 min, and 10 min pre-dose in Period 3. All other ECGs are triplicate. DI and D5 schedule in Table 2.
Blood pressure and pulse rate	X		X				X	X			X	DI and D5 schedule in Table 2 .
HIV, HBsAg, HBsAb, HBcAbHCVAb	X											
COVID-19 related procedures	X	X	→	→	→	→	→	→	X	X	X	
 Performed per local procedures.

Table 1. Study Schedule of Assessment

Visit Identifier: Abbreviations used in this table may be found in Appendix 11 .	Sci'een	Periods 1-3							Periods 4-7	F/U 28-35 days aftel' last dose	ET	Notes
Days Relative to Day 1 for each period	Day- 28 to Day-2	Day-1	Day1	Day2	Day3	Day4	Day5	Day6	Day7	Day1		
Hom's Aftel' Dose			0	24	48							
Study intervention administration			X	X	X	X	X			X		
 For Periods 1-3: QL2 hours on Days 1-4; on Day 5 only the morning dose of study drug will be administered. The washout between last dose in previous period is 7 days (Periods 2 and 3 only). Periods 1 and 2 are dosed in the fed state and Period 3 is dosed in the fasted state.
Palatability Assessments										X		
 Palatability assessments will be completed at 1 min (immediately following dose), 5 min, 10 min, and 20 min after tasting dose in vehicle. There is an at least 60 minute washout between tasting each dose in vehicle.
Pharmacokinetic blood sampling			X	X	X	X	X	X			X	D2, D3, and D4 PK samples to be drawn before AM dosing. DI and D5 PK schedule in Table 2 .
Retained Research Sample for Genetics (Prep DI)			X									Prep DI Retained Research Samples for Genetics: If not collected on the designated collection day, collect at the next available time point when biospecimens are being collected in conjunction with a participant visit. To be collected during Period 1 only.

Table 1. Study Schedule of Assessment

Visit Identifier: Abbreviations used in this table may be found in Appendix 11 .	Screen	Periods 1-3							Periods 4-7	F/U 28-35 days afte'l' last dose	ET	Notes	

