(diastolic), the BP should be repeated 2 more times and the average of the 3 BP values should be used to determine the participant's eligibility.

9. Standard 12-lead ECG that demonstrates clinically relevant abnormalities that may affect participant safety or interpretation of study results (eg, QTcF >450 ms, complete LBBB, signs of an acute or indeterminate- age myocardial infarction, ST-T interval changes suggestive of myocardial ischemia, second- or third- degree AV block, or serious bradyarrhythmias or tachyarrhythmias). If the uncorrected QT interval is >450 ms, this interval should be rate-corrected using the Fridericia method only and the resulting QTcF should be used for decision making and reporting. If QTcF exceeds 450 ms, or QRS exceeds 120 ms, the ECG should be repeated twice and the average of the 3 QTcF or QRS values used to determine the participant's eligibility. Computer-interpreted ECGs should be overread by a physician experienced in reading ECGs before excluding a participant.
10. Participants with **ANY** of the following abnormalities in clinical laboratory tests at screening, as assessed by the study-specific laboratory and confirmed by a single repeat test, if deemed necessary:
 - eGFR <60 mL/min/1.73m² based on CKD-EPI equation;
 - AST **or** ALT level $\geq 1.5 \times$ ULN;
 - Gamma-GT $>$ ULN;
 - Alkaline phosphatase $>$ ULN;
 - Total bilirubin level $\geq 1.5 \times$ ULN; participants with a history of Gilbert's syndrome may have direct bilirubin measured and would be eligible for this study provided the direct bilirubin level is \leq ULN.

Other Exclusion Criteria:

11. History of alcohol abuse or binge drinking and/or any other illicit drug use or dependence within 6 months of Screening. Binge drinking is defined as a pattern of 5 (male) and 4 (female) or more alcoholic drinks in about 2 hours. As a general rule, alcohol intake should not exceed 14 units per week (1 unit = 8 ounces (240 mL) beer, 1 ounce (30 mL) of 40% spirit, or 3 ounces (90 mL) of wine).
12. Blood donation (excluding plasma donations) of approximately 1 pint (500 mL) or more within 60 days prior to dosing.
13. History of sensitivity to sisunatovir or any of the formulation components.
14. Use of tobacco or nicotine-containing products in excess of the equivalent of 5 cigarettes/day or 2 chews of tobacco/day.

15. Unwilling or unable to comply with the criteria in the Lifestyle Considerations section of this protocol.

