7.1.1. ECG Changes

A participant who meets either bulleted criteria based on the average of triplicate ECG readings will be withdrawn from the study intervention.

- QTcF >500 ms.
- Change from baseline: QTcF >60 ms.

If a clinically significant finding is identified (including, but not limited to, changes from baseline in QTcF after enrollment), the investigator or qualified designee will determine if the participant can continue in the study and if any change in participant management is needed. This review of the ECG printed at the time of collection must be documented. Any new clinically relevant finding should be reported as an AE.

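### Protocol 8.3.3 keeps two overlapping repeat-ECG rules with different actions, and neither QTcF trigger covers a mean rise above 60 ms to 450 ms or less, although Section 7.1.1 withdraws on it

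*Protocol*

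**What the plan says.** **Repeat ECGs (Protocol 8.3.3).** Two consecutive paragraphs open with the same sentence.

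- In the first paragraph, trigger (a) is a postdose QTcF at least 60 ms above baseline and above 450 ms. Trigger (b) is an absolute QT of 500 ms or more. On either, "then 2 additional ECGs will be collected approximately 2 to 4 minutes apart to confirm the original measurement". Hourly single ECGs follow only if the repeats stay above threshold.
- In the second paragraph, trigger (a) applies when "the mean value from the triplicate measurements for any postdose QTcF interval is increased by" at least 60 ms and exceeds 450 ms. Trigger (b) is unchanged. The action differs: "then a single ECG measurement must be repeated at least hourly until QTcF values from 2 successive ECGs fall below the threshold value" that set off the repeat.

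**Format.** After the screening and pre-dose recordings, the Schedule of Activities states: "All other ECGs are triplicate".

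**Withdrawal (Protocol 7.1.1).** "A participant who meets either bulleted criteria based on the average of triplicate ECG readings will be withdrawn from the study intervention". The criteria are QTcF above 500 ms, or "Change from baseline: QTcF >60 ms". The change criterion has no absolute floor.

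**Escalation (Protocol 8.3.3).** Continuous monitoring applies if the 60 ms and 450 ms condition, or the 500 ms QT condition, lasts more than 4 hours. It also applies without a floor if the "QTcF value get progressively longer, the participant should undergo continuous ECG monitoring". The section then allows repeats to be skipped when a qualified medical provider judges a prolonged machine-read QTcF to be acceptable.

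**The concern.** There are two separate problems.

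1. Site staff have two rules for the same triplicate recording and no statement of which governs. Two people can handle the same reading differently and each be following the protocol.
2. The repeat triggers and the withdrawal criterion do not line up. A rise that the protocol considers large enough to stop dosing need not lead to any mandated ECG until it resolves. Elsewhere the protocol treats such a rise as important whatever the absolute value. The QTcF table in Section 9.3.2.1 classes an increase above 60 ms as severe, and Appendix 8 lists a 60 ms rise as a possible adverse event.

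The setting gives this some weight. Participants are healthy, and 400 mg every 12 hours is above the highest multiple dose tested so far, 350 mg (Section 4.2). Section 2.2.4 gives a Tmax of 5 to 6 hours and a half-life of 7 to 10 hours, while postdose ECGs start at 1 hour. A participant who meets the criterion at an early time point may therefore still have rising concentrations. Section 7.1 adds that a participant who permanently discontinues does not stay in the study for further evaluation, so the remaining scheduled ECGs cannot be relied on.

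**Working it through.** The plan states no figure to reproduce. The check sets the rules side by side and uses the Fridericia relation in SAP 3.5.4, rearranged as QT = QTcF × (60/HR)^(1/3).

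**Step 1. The two actions.** Suppose an exceedance is already gone at the first repeat.

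- The confirmatory rule ends after 2 ECGs. If the 2 to 4 minute spacing also runs from the original recording (an assumption, since the text does not say), that takes 2 × 2 to 2 × 4, or about 4 to 8 minutes.
- The hourly rule needs 2 successive values below threshold at up to hourly spacing, so up to about 2 hours.

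**Step 2. Where withdrawal applies but repeat trigger (a) does not.** Withdrawal on change needs QTcF > baseline + 60. Trigger (a) also needs QTcF > 450. The uncovered range runs from baseline + 60 up to 450, so its width is 450 − (baseline + 60) = 390 − baseline.

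| Baseline (ms) | Width of uncovered range (ms) |
|---|---|
| 360 | 30 |
| 370 | 20 |
| 380 | 10 |
| 385 | 5 |
| 390 or more | 0 |

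**Step 3. Worked cases.**

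| Baseline → triplicate mean (ms) | Rise | Withdrawn under 7.1.1 | Trigger (a) |
|---|---|---|---|
| 380 → 445 | +65 | yes | no |
| 385 → 450 | +65 | yes | no |
| 395 → 456 | +61 | yes | yes |
| 395 → 455 | +60 | no | yes |

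The last row shows a further small mismatch: one rule uses at least 60 ms and the other uses more than 60 ms.

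**Step 4. Can trigger (b) close the gap?**

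- If absolute QT means QTcF, it cannot, because a value of 450 ms or less is never 500 ms or more.
- If it means uncorrected QT, the 380 → 445 case at 65 bpm gives QT = 445 × (60/65)^(1/3) = 433 ms, so (b) does not fire. QT reaches 500 ms only when HR ≤ 60 × (QTcF/500)^3. That is 60 × 0.90^3 = 43.7 bpm at QTcF 450, and 60 × 0.89^3 = 42.3 bpm at QTcF 445.

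Trigger (b) therefore catches these cases only incidentally, at about 44 bpm or less.

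**Step 5. What absolute QT means.** Sections 5.2 and 9.3.2.1 write uncorrected QT when they mean it. For screening, Section 5.2 adds that "this interval should be rate-corrected using the Fridericia method only and the resulting QTcF should be used for decision making and reporting". Section 9.3.2.1 and Appendix 8 attach the word absolute to QTcF. The 8.3.3 stopping rule compares QTc or QTcF with the triggering threshold. If (b) is uncorrected QT, that mixes two quantities: QT 500 ms at 50 bpm is QTcF 500 × (50/60)^(1/3) ≈ 470 ms, already below 500 when the rule fires.

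**The case against.** **The two rules do not contradict each other.** A reader might infer that the site cannot comply with both. It can, by taking the two confirmatory ECGs and also going hourly. The paragraphs look like single-ECG and triplicate variants that were both left in, and the triplicate one fits the schedule and Section 7.1.1. This stands. What remains is that the text does not choose.

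**The triggers need not differ.** If a postdose QTcF in the first paragraph means one tracing, then baseline 400 ms with tracings 455, 458 and 462 ms sets off the first rule (462 is +62) but not the second (mean 458.3, +58.3). Section 9.3.2.1, however, takes the replicate mean as the single observation at a time point for analysis. On that convention the triggers coincide. The documents do not establish a difference.

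**The 450 ms floor can be defended.** Every uncovered value is at or below the limit that Section 5.2 accepts for entry. Stopping drug on change alone, while reserving hourly ECGs for change plus a high value, is a coherent position, and nothing in the protocol requires the two sets of criteria to match. But the protocol does not give that reasoning, and its own severity table grades the rise without a floor.

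**Follow-up exists.** A reader might infer that the withdrawn participant goes unmonitored. The documents do not support that. The value is already a mean of three tracings, and withdrawal is unaffected. There is an early-termination ECG, documented investigator review (7.1.1), adverse-event follow-up (8.4.3), unscheduled measurements (8.3), and floor-free continuous monitoring for progressive lengthening. None of these sets a repeat interval or a QTcF stopping value.

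**Repeats are not absolute anyway.** The over-read provision in 8.3.3 lets a qualified provider waive them for machine-read prolongation. That softens the minutes-versus-hours contrast but does not choose between the rules.

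**Conclusion.** Both parts hold as a minor safety-conduct point.

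- **Duplicate rule.** Section 8.3.3 prescribes two different actions at the same thresholds for the same triplicate recordings, without saying which governs.
- **Trigger gap.** A triplicate-mean rise above 60 ms to 450 ms or less mandates withdrawal but no repeat ECGs. It is possible for any baseline below 390 ms and is 390 minus baseline wide. The only exception is incidental, at about 44 bpm or less, if absolute QT means uncorrected QT.

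A reader might infer a second gap, at QTcF above 500 ms with a rise below 60 ms. It exists only on the uncorrected reading. With baseline assumed to be at most 450 ms, it needs a baseline above 440 ms, a QTcF between 500 and 510 ms, and a heart rate above roughly 60 to 64 bpm (60 × (501/500)^3 = 60.4; 60 × (510/500)^3 = 63.7). It disappears if the term means QTcF, so it is a reason to define the term and not a finding in itself.

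The cases should be rare, and the documents give no data for a frequency. The effect on endpoint summaries is negligible: anyone in the gap is already in the above-60 ms category on the triplicate mean.

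**What to change.** In Protocol 8.3.3:

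1. Keep the triplicate-mean paragraph as the rule for scheduled ECGs. Limit the two-confirmatory-ECG paragraph to unscheduled single ECGs, or delete it. Limiting it is safer, because Section 8.3 allows unscheduled measurements and a single tracing still needs a confirmation rule.
2. Add the 7.1.1 withdrawal criteria as triggers for hourly repeats: a triplicate-mean QTcF rise above 60 ms with no floor, or QTcF above 500 ms. Repeats continue until 2 successive values fall below the triggering threshold.
3. State that trigger (b) is QTcF, or give it a stopping value in QT.

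Leave the continuous-monitoring and cardiologist criteria unchanged. Removing the floor there could send a participant who goes from 360 to 421 ms (+61) and stays there for more than 4 hours to continuous monitoring, and to a cardiologist if unresolved at 8 hours. That trade-off is debatable and the gap does not require it.

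The cost is a few extra ECGs in rare cases, with no added visits and no SAP change. The wording goes through the normal amendment process in Section 10.1.1: ethics approval if it counts as a change to study design, and health-authority approval if it is substantial.
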